Statistical Analyses	
Cross-sectional analyses will include a comparison of FM patients with HC with respect to GABA, Glx and other neuroimaging biomarkers (t-tests, linear regression);
 
Longitudinal analysis will study treatment effects on within-patient change in neuroimaging biomarkers and changes in clinical pain (t-tests, linear regression with change as a response, linear mixed model with biomarker as a response); treatment and biomarker predictive effects at baseline on clinically relevant 50% reduction of pain as a binary response (logistic regression); the effects of treatment and biomarker baseline measurements on within-patient change in DMN-insula connectivity; biomarker mediation analysis for the treatment effect.
 
In order to screen neuroimaging biomarkers that respond to treatment (show reduced DMN-insula connectivity), interim testing for futility will be performed.
 
Reasons for missingness will be analyzed using multinomial logistic regression with treatment as one of the covariates. The results of formal missing data imputation by predictive-matching algorithms will be compared to the results of missing data exclusion in a sensitivity analysis.

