11. STATISTICAL CONSIDERATIONS

11.1. Aim 1: At baseline, characterize altered somatosensory neurocircuitry underlying chronic pain in FM.

Hypothesis 1: Using resting fcMRI, the insula in FM patients will show more correlation with DMN, and more anti-correlation with SMN, compared to HC.

We will use dual-regression independent component analysis (ICA) to evaluate resting connectivity between DMN/SMN and insula. Two-sample t-tests will compare FM vs. HC, cluster-corrected at $p=0.05$.

Based on our previous studies, assuming DMN connectivity z score (middle insula region) of 1 for a fibromyalgia patient vs. 0.5 for a healthy control with a common standard deviation of 0.5, we will expect a typical relative effect of 1 (mean ICA-derived z score over its standard deviation). Similar effects (negative connectivity values) are expected for SMN-derived biomarkers. With the planned numbers of subjects we will have the power exceeding 97% to detect the effects by a two-sided t-test.

Hypothesis 2: Using $^1\text{H-MRS}$, FM patients will show pain related increased Glx and reduced levels of GABA within the insula and S2 as compared to HC.

Metabolite concentration from regions of interest will be assessed using spectra data input into LCModel. A two-sample T-test will compare FM vs. HC, significant at $p=0.05$.

Our sample size calculation for difference between FM and HC assumes (from pilot data) that Glx, a proxy for glutamate concentration, has mean(SD) = 10.5(1.4) in arbitrary institutional units (AIU) and a FM-HC relative difference in excess of 10%. Thus we conservatively hypothesize an average Glx around 11.5 AIU and GABA around 1.3 mmol/kg in the FM group. We conclude that we will have the power of at least 84% for the GABA and 81% for the Glx based on a two-sided t-test with unequal N (80 in FM vs. 20 in HC) at the significance level of 0.05.

Hypothesis 3: Using evoked pain fMRI, FM patients will be more sensitive to evoked pressure pain and demonstrate greater insula activation to pain stimuli, compared to HC.

A general linear model will assess brain response to experimental pain from a block design BOLD fMRI run. A group level FM - HC difference map will use a two sample t-test, cluster corrected at $p=0.05$.

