This aim evaluates a *mechanistic* value of the neuroimaging biomarkers by studying their response to treatment and correlation between the change in biomarker measurements and changes in pain induced by treatments, and biomarker mediation effects.

Hypothesis 1: EA, which involves greater somatosensory afference, will more readily reduce resting insula connectivity to SMN and DMN compared to ML. The change in pain will correlate with change in insula connectivity for EA, but not ML. Insula connectivity will represent a mediator for the treatment effect.

Treatment effects on connectivity

We will perform dual-regression ICA with group level estimates for baseline and post-treatment fcMRI data (DMN and SMN) entered into a linear mixed model with factors STIM (levels EA, ML) and TIME (levels baseline and post-therapy). Time by treatment interaction effect will be of main interest in the analysis. If a significant main effect or interaction is found, we will perform post-hoc difference map analyses, to evaluate which group produced the greatest change in resting connectivity.

Power analysis for fcMRI is based on data from the preliminary study on intrinsic connectivity and its short-term response to acupuncture. From preliminary data on 15 subjects, we estimate the SD of the number of voxels activated before and after acupuncture in the default mode independent component to be 2860 and 4559, respectively. The covariance between these before and after counts is 3388878. This implies the standard deviation of the within-subject change in connectivity of $\sqrt{2860^2+4559^2-2*3388878}=4710$. Based on the same data, we find the before and after means to be 7078 and 9844, respectively. Then, a two-sided paired t-test for the presence of change will have the effect size of 0.6 and the power of 95% with 40 patients in the EA group.

Based the similar mean connectivity difference of around 3000 between ML and EA, and the same SD of 4710 we will have 80% power to detect the difference between treatments with respect to the mean within-patient change in connectivity.

Correlation with pain

A linear mixed model will be used to regress BPI pain measurements on the neuro-imaging biomarkers. Correlation between clinical pain and biomarkers is the primary target.

We hypothesize a correlation coefficient of at least 0.5 between pain and connectivity z score in the EA arm. This will give us 94% power to detect the correlation.

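### The 80% and 95% power figures for the Aim 2 connectivity endpoint are computed correctly, but on default-mode voxel counts from a short-term study, so they are not shown to apply to the insula connectivity change being tested

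*Combined protocol and SAP*

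**What the plan says.** Section 11.2, Aim 2 Hypothesis 1, states that EA "will more readily reduce resting insula connectivity to SMN and DMN compared to ML". The Synopsis describes biomarkers that respond to treatment in the same direction, as those that "show reduced DMN-insula connectivity". The model is a linear mixed model on dual-regression ICA estimates at baseline and after therapy, and "Time by treatment interaction effect will be of main interest in the analysis".

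The power paragraph under the same hypothesis draws on a preliminary study of short-term response to acupuncture in 15 subjects. There, "we estimate the SD of the number of voxels activated before and after acupuncture in the default mode independent component", giving 2860 and 4559 with a covariance of 3388878. From the same data, "we find the before and after means to be 7078 and 9844, respectively". The plan derives an SD of change of 4710 and 95% power for a paired test with 40 EA patients. It then continues: "Based the similar mean connectivity difference of around 3000 between ML and EA", keeps the SD of 4710, and states 80% power.

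Elsewhere connectivity is on another scale. Section 11.1 (Aim 1, Hypothesis 1) works by "assuming DMN connectivity z score (middle insula region) of 1 for a fibromyalgia patient vs. 0.5 for a healthy control" with an SD of 0.5. The correlation paragraph of Section 11.2 reads: "We hypothesize a correlation coefficient of at least 0.5 between pain and connectivity z score in the EA arm". The mediation power paragraph goes back to voxels, with a treatment coefficient of 3000, an SD of change of 4500 and 81% power.

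**The concern.** The power inputs differ from the endpoint in three ways.

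- **Quantity.** The number of voxels in the default-mode component measures the spatial extent of a whole network. The hypothesis concerns how strongly the insula is coupled to that network and to the SMN. The SMN has no power statement for the treatment comparison.
- **Time frame.** The inputs describe a short-term response. The trial measures change after eight treatments over four weeks, and Section 9.3.1 itself separates acute findings from the longitudinal question.
- **Direction.** The voxel count rose. The endpoint is expected to fall, and Section 9.3.1 reports that a longitudinal course of manual or sham acupuncture lowered DMN-insula connectivity.

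This is the only power statement for the randomised connectivity comparison. If it does not carry over to the endpoint, a reader cannot tell what EA-ML difference 40 per arm can detect, and a null result could be read as stronger evidence of no effect than it is.

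**Working it through.** **Inputs.** From Section 11.2: SDs 2860 and 4559, covariance 3388878, means 7078 and 9844, assumed EA-ML difference 3000. From the Synopsis: 40 per arm. The power paragraph gives no alpha, so two-sided 0.05 is carried over from Section 11.1. No dropout is allowed for.

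**1. Reproducing the plan's figures (noncentral t)**
- SD of change = √(2860² + 4559² − 2 × 3388878) = 4710.
- Pilot change = 9844 − 7078 = +2766. Standardised, 2766 / 4710 = 0.587, which the plan rounds to 0.6.
- Paired test, n = 40, effect 0.587: 95.2%. The stated 95% reproduces.
- Two-sample test of mean change, 40 per arm, 3000 / 4710 = 0.637: 80.3% (81.3% by normal approximation). The stated 80% reproduces.

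With two time points and complete data, the time-by-treatment interaction is the comparison of mean change, so the test form also matches.

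**2. Sensitivity to the rounded difference**
- At 2766 instead of 3000, SD 4710, 40 per arm: 73.7% (74.7% by normal approximation).
- Standard error of the pilot change = 4710 / √15 = 1216. The gap of 234 between 3000 and 2766 is 0.19 standard errors.

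**3. The endpoint scale**

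Power on the insula z score cannot be computed: the documents give neither an SD of within-patient change nor an expected EA-ML difference in z. A detectable difference can be given conditionally. At 80% power, two-sided 0.05 and 40 per arm it is 0.634 × SD of change.

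SD of change = √(s₁² + s₂² − 2·r·s₁·s₂). Take s₁ = 0.5, the cross-sectional SD in Section 11.1. The pre-post correlation r is an assumption. Its low end is the pilot value, 3388878 / (2860 × 4559) = 0.26. Its high end, 0.7, has no source in the documents.

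| Post-treatment SD | r | SD of change (z) | Detectable difference (z) |
|---|---|---|---|
| 0.5 (equal) | 0.7 | 0.39 | 0.25 |
| 0.5 (equal) | 0.26 | 0.61 | 0.39 |
| 0.80 (pilot ratio 4559 / 2860 = 1.59) | 0.7 | 0.57 | 0.36 |
| 0.80 (pilot ratio) | 0.26 | 0.82 | 0.52 |

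For scale, Section 11.1 assumes an FM-HC gap of 1 − 0.5 = 0.5 z. The detectable EA-ML difference runs from about half of that gap (0.25 / 0.5) to slightly more than all of it (0.52 / 0.5).

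**4. Baseline adjustment, on the plan's own pilot inputs**
- Adjusted SD = 4559 × √(1 − 0.26²) = 4402, against 4710 for change scores.
- Power at 3000: 80.3% becomes 85.3%. At 2766: 73.7% becomes 79.2%.

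**The case against.** Much can be said for the plan, and several stronger readings fail.

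- A reader might infer an arithmetic error. There is none; every stated figure reproduces.
- A reader might infer that 3000 was inflated to reach 80% and that 74% is the true power. The plan marks the value as approximate, a planning difference need not equal a pilot estimate, and 234 voxels is far inside a standard error of 1216. The 74% is a sensitivity value, not a correction.
- A reader might object that using a one-group change as the between-arm difference hides an assumption of no change under ML. Section 5 states exactly that as the hypothesis (Aim 2, Hypothesis 1).
- A reader might infer that the rise in the pilot invalidates the 80%. Two-sided power does not depend on sign. The rise bears only on whether the pilot measure is relevant.
- It can also be argued that power depends only on the standardised effect, about 0.64, which might hold on the z scale too. It might, but nothing in the documents shows that it does.

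Three limits on the criticism stand. The Aim 2 model sentence does not itself name a z score; that scale comes from Section 11.1 and from the correlation paragraph. Section 9.3.1 plans voxel-wise, cluster-corrected maps, so a single-region t-test is itself a simplification. And the adjustment gain in step 4 is measured on voxel counts, so its size on the z scale is unknown.

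**Conclusion.** The point holds as an endpoint mismatch. The 80% between arms and 95% within EA are correct for the spatial extent of the default-mode component under short-term stimulation. They are not shown for the change in DMN- or SMN-insula connectivity after eight treatments. The mediation power of 81% rests on the same kind of voxel inputs and has the same gap.

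The documents do not support saying that the trial is underpowered for this endpoint, because true power on the z score is unknown. The detectable differences of 0.25 to 0.39 z and 0.36 to 0.52 z are illustrative. They rest on a baseline SD of 0.5, an assumed correlation of 0.7 to 0.26, the stated SD ratios, alpha 0.05, a single-region test and no dropout. The randomised comparison itself remains valid; only its stated power lacks support.

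**What to change.** 1. In Section 11.2, withdraw the 80% and 95% as power for insula connectivity, or label them as voxel-extent figures from a short-term study. If they stay, give 74% at the unrounded change of 2766 as a sensitivity value. Add the detectable EA-ML difference on the insula z score at 40 per arm, as 0.63 times the SD of change, with the two illustrative ranges and their assumptions beside it.
2. Restate the mediation power on the same scale, or flag that its 3000 and 4500 are voxel counts and that the 81% is not shown for insula connectivity.
3. For the extracted insula connectivity values, compare arms on post-treatment connectivity adjusted for baseline. Baseline scans are already planned for every FM patient. The pilot inputs suggest a gain of about five percentage points, with the size on the z scale to be seen.

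The cost is SAP wording and one model specification. No patients, visits or scans are added. The power statement becomes less definite.

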9.3.1. Functional connectivity MRI

Resting 6min scans, performed with subjects resting comfortably in the scanner with eyes open, will be completed at the beginning of the scan session. In order to quantify intrinsic brain connectivity, functional MRI data will be analyzed with both a dual-regression ICA approach and seed-voxel approach. These approaches are complementary, as they quantify intrinsic brain connectivity on a network level (dual regression pICA) and a more specific region-focused level (seed-voxel). Physiological data will also be collected simultaneously to the fcMRI data, as cardio-respiratory fluctuations are known to influence fMRI intrinsic connectivity estimation within several brain networks [95, 96]. A similar approach will be used to evaluate the sustained cuff pain 6min scan.

Dual Regression ICA Approach: The within- and between-subject resting fMRI data analysis will be performed using ICA through Multivariate Exploratory Linear Optimized Decomposition into Independent Components (MELODIC, an FSL tool) and a previously validated dual regression approach [97]. This technique allows for voxel-wise comparisons of resting state functional connectivity by first temporally concatenating resting fMRI data from all subjects, followed by back-reconstructing the group networks for individual subjects, which are then used for within- and between-subject group and difference maps. This technique does not regress out global signal (enhancing interpretation of anti-correlations), and has been found to have moderate to high test-retest reliability in previous studies [98]. This process will be completed for networks of interest (DMN, SMN). The MVN will also be evaluated as a control network. Group analyses will be performed to evaluate intrinsic brain connectivity differences between FM and HC groups, how this intrinsic connectivity covaries with spontaneous pain intensity in FM patients, and how networks differentially change following EA and ML. The results will be threshold at $p < 0.05$, cluster-corrected for multiple comparisons.

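### Section 11.2 compares EA with ML on unadjusted change in connectivity; adjusting for each patient's baseline scan would raise power from 80% to about 85% at the pilot correlation, with a negligible worst-case loss

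*Combined protocol and SAP*

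**What the plan says.** Section 11.2 (Aim 2, Hypothesis 1, treatment effects on connectivity) has the baseline and post-treatment estimates "entered into a linear mixed model with factors STIM (levels EA, ML) and TIME (levels baseline and post-therapy"), and adds: "Time by treatment interaction effect will be of main interest in the analysis". No baseline covariate is listed.

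The power calculation uses the raw within-patient change. The inputs are pilot figures: "From preliminary data on 15 subjects, we estimate the SD of the number of voxels activated before and after acupuncture", namely 2860 and 4559, and "The covariance between these before and after counts is 3388878". From these the plan derives a change SD of 4710. With a difference of about 3000 between ML and EA it concludes that "we will have 80% power to detect the difference between treatments with respect to the mean within-patient change in connectivity".

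The Synopsis lists, among several longitudinal analyses and without ranking them, "the effects of treatment and biomarker baseline measurements on within-patient change in DMN-insula connectivity". Section 11.2 does not describe such a model.

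**The concern.** With two visits, complete data and a free treatment factor, the time-by-treatment interaction is the difference between arms in mean change. A change score fixes the coefficient on baseline at 1. The plan's own pilot figures put that coefficient at about 0.41, so the planned contrast over-corrects for baseline and carries avoidable variance. Regression on baseline estimates the coefficient instead.

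This is the randomised test of the first mechanistic hypothesis. It is planned at 80% with all 40 patients per arm evaluable, and no dropout allowance is stated. Its power also depends strongly on the pre-post correlation, which the plan knows only from 15 subjects.

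**Working it through.** **Inputs.** From Section 11.2: SD before 2860, SD after 4559, covariance 3388878, pilot n = 15, difference 3000. From the Synopsis: 40 per arm. Assumed: two-sided alpha 0.05 (Section 11.2 gives no level for this contrast).

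**1. The plan's figure.**
- Change SD = √(2860² + 4559² − 2 × 3388878) = 4710.
- Standard error of the difference = 4710 × √(2/40) = 1053; 3000/1053 = 2.85.
- Noncentral t with 78 df gives 80.3%, so the stated 80% is reproduced.

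**2. What the pilot says about baseline.**
- r = 3388878/(2860 × 4559) = 0.26.
- Fisher 95% interval with n = 15: tanh(atanh 0.26 ± 1.96/√12) = −0.29 to 0.68.
- Slope of post on baseline = 3388878/2860² = 0.41. With these SDs a slope of 1 would need r = 2860/4559 = 0.63.

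**3. Adjusted analysis at the pilot r.**
- Residual SD = 4559 × √(1 − 0.26²) = 4402.
- Variance is inflated by 1 + 1/(2n − 4) = 1 + 1/76 for estimating the slope, so SE = 4402 × √(2/40 × 77/76) = 991; 3000/991 = 3.03.
- Noncentral t with 77 df gives 84.8%. A simulation of 20,000 trials gave 80.4% unadjusted and 84.8% adjusted, with type I error of 4.8% to 5.3% for both.

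**4. Range over r** (pilot SDs fixed, 40 per arm):

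| r | Unadjusted | Adjusted |
|---|---|---|
| −0.29 | 59.2% | 85.5% |
| 0 | 69.2% | 82.3% |
| 0.1 | 73.3% | 82.7% |
| 0.2 | 77.6% | 83.8% |
| 0.26 | 80.3% | 84.8% |
| 0.4 | 86.8% | 88.3% |
| 0.5 | 91.3% | 91.5% |
| 0.6 | 95.3% | 95.0% |
| 0.68 | 97.7% | 97.6% |

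**5. In patients, at r = 0.26.** With 36 evaluable per arm (10% loss, assumed), power is 76.0% unadjusted and 80.8% adjusted. Matching the adjusted power of 40 per arm without adjustment takes 45 to 46 per arm (84.8%, 85.6%).

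**6. If the SDs are equal at both visits (assumed).** The ratio of adjusted to change-score variance is s²(1 − r²)/[2s²(1 − r)] = (1 + r)/2, which is 63% at r = 0.26, 75% at 0.5 and 85% at 0.7. Holding the change SD at 4710, adjusted power is 94.1%, 89.7% and 85.8%, against 80.3% unadjusted.

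**The case against.** The strongest objection is that nothing is wrong: the plan names a valid test, uses the matching SD and reaches a conventional target. That is true, and the point is one of efficiency only.

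The second is that the Synopsis may already intend the adjustment. It may, but the clause does not say that the covariate is the outcome's own baseline. It could equally describe a separate prediction analysis, and Section 11.2 names a different main contrast.

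The third is that the pilot figures may not transfer. They describe a whole-component voxel count after short-term acupuncture, and that count rose (7078 to 9844), whereas the hypothesis is a fall in insula connectivity after four weeks. Section 9.3.1 says the dual-regression method "has been found to have moderate to high test-retest reliability in previous studies", so r may be well above 0.26 and the negative end of the interval is unlikely. This stands: 85% is an illustration from the plan's own inputs, not a forecast. It does not favour the unadjusted test. At higher r with the pilot SDs the two tests nearly coincide, and with equal SDs adjustment still gains.

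The fourth is that connectivity is analysed in cluster-corrected maps, to which a single-endpoint power calculation does not apply. This also stands, so the recommendation covers only a per-patient summary. The plan's own power figure is of that kind, and Section 11.1 uses another per-patient value, "assuming DMN connectivity z score (middle insula region) of 1 for a fibromyalgia patient".

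**Conclusion.** The concern holds as a missed gain in efficiency. Section 11.2 names no baseline covariate for the EA-versus-ML contrast. On the plan's figures, adjustment raises power from 80% to about 85% at r = 0.26. With the pilot SDs the gain runs from about 13 points at r = 0 to almost nothing from r = 0.5, and the largest loss is about 0.2 points near r = 0.6 (0.3 points with 36 per arm). Across the whole interval for r, adjusted power stays at 82% or more, while unadjusted power is 69% at r = 0 and 59% at the lower limit.

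This rests on a difference of 3000, complete data, two-sided alpha 0.05 and transfer of the pilot SDs. Confidence in the direction is high; confidence in the size of the gain is moderate, because r and the SDs come from 15 subjects on a different measure. The change should be made, but the trial's validity does not depend on it.

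**What to change.** In Section 11.2:

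- Name the per-patient connectivity summary for the EA-versus-ML test, for example the middle-insula DMN z score of Section 11.1 or the dual-regression estimates used in Section 11.3.
- Make the main contrast the treatment coefficient from a regression of the post-treatment value (equivalently, the change) on treatment and the same measure at baseline. A mixed model with a common baseline mean for the two arms would also serve.
- Keep the unadjusted interaction as a sensitivity analysis.
- State whether the Synopsis clause refers to this analysis.
- Report power as a range over r.
- Leave the voxel-wise and post-hoc difference maps as planned.

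Hypotheses 2 and 3 of Aim 2 follow the same modelling approach, so the sponsor should say whether the adjustment extends to Glx, GABA and evoked-pain activation.

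The cost is SAP wording and one degree of freedom. No new data are needed. Fixing the choice now also prevents a later choice between adjusted and unadjusted results.

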Interim analysis. After 50% of the subjects have been enrolled and evaluated, we will determine if fcMRI outcome metrics are sensitive enough to continue using for the biomarker for the duration of the study. Screening of biomarkers (brain regions) will be done by computing a post-hoc power based on 20 patients per arm. Biomarkers showing post-hoc power lower than 20% will not be pursued further. This decision corresponds to dropping biomarkers showing correlation coefficients less than 0.18 in the interim analysis.

Mediation Analysis

In the linear mixed model regressing BPI pain score on treatment and time, the effect of treatment on pain is expressed as a regression coefficient for time specific to treatment group (or a treatment by time interaction). Mediation effect will be measured as the proportion of treatment effect explained by the biomarker (PTE) representing a relative change in the regression coefficient when biomarker is included in the model (relative to the coefficient before biomarker inclusion into the model). Standard error for the PTE will be estimated by bootstrap, and a two-sided 95% interval for the effect will be constructed. Wald test with the statistic of the form (change in regression coefficient)/(bootstrap SE) will be used to test for the mediation effect. Similar analyses will be done using a logistic regression model with clinically relevant reduction in pain (defined as 50% and 30%) as a response.

Power. We use Sobel's test based on linear regression to compute power. Power analysis targets biomarkers with the mediation effect of PTE=0.5. We assume that the regression coefficient in the model for the treatment effect on connectivity is 3000; treatment effect beta in the model of change in pain excluding the biomarker is 2; standard deviation of the randomized treatment variable 0.5; standard deviation of the change in connectivity over time 4500 voxels; squared the correlation between the treatment variable and the change in connectivity $3.7e-05$; standard deviation of errors in the full model regressing change in pain on both treatment and the biomarker 1.5. These assumptions are consistent with the ones made previously in the power calculations related to different lags of the mediation analysis, with our preliminary data, and with the acupuncture effects on pain reported in the literature. Under these assumptions we will have the power of 81% to detect the mediation effect by Sobel's test.[114]

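### Aim 2 predicts that change in pain tracks change in the biomarker in EA but not ML, but the model written for it names no change or within-patient term and no biomarker-by-arm contrast

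*Combined protocol and SAP*

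**What the plan says.** Section 11.2, Hypothesis 1 states the target as follows: "The change in pain will correlate with change in insula connectivity for EA, but not ML". Hypotheses 2 and 3 make the same prediction for Glx/GABA and for pain-evoked insula activation. The Aim 2 heading and its opening paragraph also speak of change in pain and change in biomarker.

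Under the Correlation with pain subheading, the method is one sentence, "A linear mixed model will be used to regress BPI pain measurements on the neuro-imaging biomarkers", followed by "Correlation between clinical pain and biomarkers is the primary target". The power statement is for one arm: "We hypothesize a correlation coefficient of at least 0.5 between pain and connectivity z score in the EA arm", with 94% power. Hypothesis 2 reuses this approach. Hypothesis 3 names change with change, then carries it out by entering evoked responses as covariates in the BPI model.

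Section 11.3 (Aim 3) is more explicit for baseline predictors. It sets a change score in BPI as the outcome and contrasts the EA and ML slopes within one regression.

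**The concern.** The hypothesis has two parts that the analysis sentence does not deliver.

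- **Within-patient part.** The claim is that patients whose biomarker moves more also have pain that moves more. A regression of BPI levels on biomarker levels can also pick up patients who have both higher pain and higher connectivity at every visit. Sections 6.2.4 and 9.3.1 report such an association across patients at scan time. Section 9.3 lists variation between patients and longitudinal tracking as separate properties.
- **Arm-specific part.** Showing that an association is present in EA and absent in ML needs a comparison of the two arms. None is stated for BPI in Aim 2.

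At stake is the mechanistic reading of Aim 2. An association that predates treatment could be reported as treatment-induced changes moving together, and a chance difference in significance could be reported as specificity to EA.

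**Working it through.** **1. The plan's 94%.** Inputs from Section 11.2: r = 0.5, EA arm, n = 40. Two-sided alpha 0.05 is stated for Aim 1 and assumed here. For a regression slope on 38 df, the noncentrality is √40 × 0.5/√0.75 = 3.65, giving 94.5%. With √38 in place of √40 it is 3.56, giving 93.4%. Simulation of the correlation test gives 92.3%. The figure is sound for one EA correlation and says nothing about ML.

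**2. Judging specificity by significance in each arm.** Suppose the true change-change correlation is the same in both arms, 40 per arm. With per-arm power p, EA is significant and ML is not with probability p(1 − p):

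| Common r | p | EA significant, ML not |
|---|---|---|
| 0.1 | 9.5% | 8.6% |
| 0.2 | 24% | 18% |
| 0.3 | 48% | 25% |
| 0.4 | 74% | 19% |
| 0.5 | 92% | 7% |

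The maximum is 25%, at p = 50%. An arm-by-biomarker-change interaction rejects in about 5% of trials in every row. No ICC is needed here.

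**3. Mixing of between- and within-patient association.** Two visits were simulated, with a stable patient component in the biomarker and in BPI, correlation r between those components, and uncorrelated visit noise. The true change-change correlation is therefore zero. The fitted model is one literal reading of the sentence: random intercept, time, raw biomarker, EA arm only (n = 40), t on 38 df.

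The one ICC input available comes from the power text. The SDs there are 2860 and 4559 ("From preliminary data on 15 subjects, we estimate the SD of the number of voxels activated before and after acupuncture") and "The covariance between these before and after counts is 3388878". So the pre-post correlation is 3388878/(2860 × 4559) = 0.26. Its Fisher-z 95% range with n = 15 is −0.29 to 0.68. The BPI ICC and r are assumed.

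| Biomarker / BPI ICC | r = 0.1 | r = 0.3 | r = 0.5 |
|---|---|---|---|
| 0.26 / 0.26 | 5.6% | 8.8% | 15.6% |
| 0.26 / 0.5 | 6.0% | 9.1% | 18.2% |
| 0.5 / 0.5 | 6.3% | 15.7% | 35.0% |

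With r = 0 the same model rejects in 5.1-5.4%. Regressing change on change rejects in 4.7-5.3%.

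**4. Power for the contrast the hypothesis implies.** Take EA 0.5 against an assumed ML value of 0, 40 per arm. Fisher z: 0.5493/√(2/37) = 2.36, and Φ(2.36 − 1.96) gives 66% (simulation 67%). The interaction test gives about 63% by simulation. If the ML correlation is 0.1, 0.2 or 0.3, the Fisher-z figure falls to 49%, 32% or 18%.

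**The case against.** The strongest reply is that the target is not in doubt. The Aim 2 heading, its opening paragraph and Hypothesis 3 all say change with change. The synopsis lists regression with change as a response. The analysis sentence names no random effects or covariates, so it does not commit the team to a raw-biomarker random-intercept model. No passage says that arm-by-arm significance will decide the claim. All of this stands, and it makes the problem one of under-specification. It does not supply the missing terms: the synopsis wording concerns treatment effects, and the EA-versus-ML slope powered under Hypothesis 3 concerns pressure pain, not BPI.

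The sizes are also open to challenge. The 0.26 comes from 15 subjects' voxel counts in a study of short-term response, not from four-week z-scores. With low r or low ICCs the inflation is negligible. At the plan's own r of 0.5 in both arms, the per-arm rule misleads in only 7% of trials, and in those trials the EA correlation is real and only the denial for ML is wrong. These limits are accepted.

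A reader might infer more than the documents support:

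- **That a wrong model was chosen.** The text leaves the model open.
- **That the 94% is an error.** It reproduces for the test it describes, and no power is claimed for the contrast.
- **That the correlation is the trial's primary endpoint.** The words "Correlation between clinical pain and biomarkers is the primary target" belong to the correlation subsection.
- **That the treatment comparison is compromised.** For that analysis the plan says "Time by treatment interaction effect will be of main interest in the analysis", and this is untouched.
- **That a real link between changes is implausible.** Sections 9.3.1 and 9.3.2 report within-patient tracking in the team's own data.

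**Conclusion.** The point holds as a specification gap that should be closed before analysis. Aim 2 states a change-with-change association specific to EA; the written model need not estimate change with change and contains no comparison of arms.

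The arm-contrast part is the firmer of the two. It needs only the assumption that specificity would otherwise be read from significance in each arm, and the resulting error is about 7% to 25% over common correlations of 0.1 to 0.5. The within-patient part depends on one reading of the sentence and on an r and a BPI ICC that the documents do not give. About 9% and 18% are illustrations at the pilot-based biomarker ICC. They grow at higher ICCs and vanish as r or the biomarker ICC approaches zero.

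**What to change.** For Hypotheses 1-3, specify a regression of change in BPI on arm, change in biomarker and arm × change in biomarker. With two complete visits, an equivalent is to split the biomarker into patient mean and within-patient deviation in the mixed model. Test the EA slope, and test the interaction for the EA-but-not-ML claim. Report the level-on-level association as descriptive. If a version adjusted for both baselines is fitted, keep it as a sensitivity analysis, since it can bring the between-patient association back. Name which BPI assessments pair with the scans, because Section 3.1 schedules BPI at both the behavioural and the MRI visits.

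State that the 94% applies to the EA-only correlation (about 92-94% by method). State also that the contrast has about 63% power by the interaction test or 66-67% by Fisher z, assuming 0 in ML.

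The data and visits do not change. The cost is an explicit test with modest power, so a non-significant interaction should not be read as equal association in the arms. Enlarging the trial is not proposed. For scale, 80% power would need about 59 evaluable patients per arm for the interaction. Fisher z gives 3 + 2(1.96 + 0.8416)²/0.5493² = 55.03, so about 55-56.

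Optional and secondary: the mediation text works from a BPI-score model ("In the linear mixed model regressing BPI pain score on treatment and time"), while its power calculation uses change in pain. Aligning them with a within-patient biomarker term would be tidier, but in simulation at biomarker ICC 0.26 that version's Wald test was conservative (1.1-1.9% rejection under the null, against 3.8-10.0% for the raw-biomarker version).
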